Table 7. Neurocognitive Assessment	
HVLT	Verbal Learning/Memory
Stroop	Attention/Executive
Trail Making A & B	Executive
COWA & Animals	Verbal Fluency
BVMT	Visual Memory
Symbol Digit Coding	Processing Speed
Letter Number Sequencing	Working Memory
PASAT	Working Memory
Digit Span	Working Memory
NIH Toolbox Subtests:	
* Dimensional Card Sort	Executive
* Flanker	Attention/Executive
* Picture Sequence	Episodic Memory
* Picture Vocabulary	Language
* Oral Reading	Language
* Pattern Comparison	Processing Speed
* List Sorting	Working Memory

6.7.1. Functional Outcomes. A touchscreen computer-based functional assessment tool will be used to measure tasks like medication management, ATM banking, prescription refill via voice menu. Task difficulty can be varied and real-time efficiency and accuracy data are collected; the measure is highly correlated with component cognitive abilities targeted in this study^{315,316}. See Appendix 2 for a detailed manual.

6.7.2. QOL and PROMIS self-reported health assessment. We will administer *the Medical Outcomes Study Short Form-36 (SF-36: v. 2.0*, a widely used QOL measure), and the PROMIS self report measures at each assessment. The PROMIS measures assess change in self-reported cognitive and physical function.^{321 321} Change in self reported physical and mental health status correlate with QOL and mental and physical health status.^{322,323 324} These two measures will serve as important assessments of interventions influence on everyday life.

6.8. Alcohol and Drug Use Questionnaires. We will administer the Alcohol Use Disorders Test (AUDIT-10) and Drug Abuse Screening Test (DAST-10). These measures will provide

valuable information about how drug and alcohol use may alter the overall efficacy to tDCS, cognitive training and education training.

6.9. Driving Record Assessment. Driving records will be requested following the completion of the intervention; records will be requested at 5 years post intervention and at 10 years post intervention. These records will allow us to examine real world driving outcomes. The driving record assessment is optional (the participant chooses to consent to this portion or not at screening). Participants who do not consent to the driving record assessment can still participate in the study.

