Timeline. Construction of the MRI-derived finite element computational models as described in aim 1 is estimated to begin in January 2021. We estimate approximately 24 months will be required to complete this process. By Q3 2022 the ACT study is anticipated to be completed and access to the currently blinded randomization conditions will be available to complete aim 2 and the exploratory aim.

The additional analyses described in section 6.18 will not impact study participation in any way. The analyses will only use data collected under currently approved study procedures.

7. Possible Discomforts and Risks:

Potential Risks.

There are minimal risks associated with participation in this study. The potential risks are as follows:

Magnetic resonance imaging (MRI). MRI is a procedure that allows doctors to look inside the body by using a scanner that sends out a strong magnetic field and radio waves. This procedure is used routinely for medical care and is very safe for most people, but participants will be monitored during the entire MRI scan in case any problems occur. The risks of MRI are:

- The MRI scanner contains a very strong magnet. Therefore, participants may not be able to have the MRI if they have any type of metal implanted in their body, for example, any pacing device (such as a heart pacer), any metal in their eyes, or certain types of heart valves or brain aneurysm clips. A MRI technologist will question participants about any contraindications before they enter the scanner.
- There is not much room inside the MRI scanner. Participants may be uncomfortable if they do not like to be in close spaces ("claustrophobia"). During the procedure, participants will be able to talk with the MRI staff through a speaker system, and, in the event of an emergency, participants can tell them to stop the scan.
- The MRI scanner produces a loud hammering noise, which has produced hearing loss in a very small number of participants. Participants will be given earplugs to reduce this risk, and headphones for added protection.
- If an obvious abnormality is discovered during the participant's MRI scan, they will be informed about it by the research team, and will be provided with a copy of the MRI scan and we will encourage them to see their primary care physician. MRI will only be done for research purposes in this study.
- Participants will be monitored very carefully while in the scanner, and repeatedly checked to ensure comfort.

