Contact information for study participants will be kept in separate files and databases from the research data. This information will be used by the research assistants to send reminders about follow-up times and appointments via phone, email, or mail correspondence depending on the participant's preference. Research assistants may contact study participants via phone, email, or mail to provide directions to the study site or answer general questions or concerns about the study. In order to avoid participants who are lost to follow up, we will contact study participants periodically between their 3 month post intervention visit and their one year follow up visit at approximately 3 month intervals. We will send a letter and/or email to participants who we are unable to contact via phone to see if their contact information has changed. The information will only be kept on computers or devices that are both password protected and encrypted. Any written forms will be kept in locked file cabinets or locked briefcases. None of the research data in the central database will have participant identity information. No results will ever be reported in a personally identifiable manner. All research data will be entered directly into a web-based survey that is maintained by the University of Florida CTSI (REDCap), and the data are encrypted as soon as they are sent in a wireless format. The data will be transferred and stored on secure servers at the University of Florida, with no identifying information. Only de-identified data will be entered into the REDCap database across all sites. A data confidentiality agreement will be signed and filed with the UF IRB before any data are collected at any site.

No survey data will be labeled with the participant's name or other identifying information, but will instead be labeled with a study ID number. Documents linking study ID numbers to identifying information (e.g., name, address, etc) will be stored electronically in a password-protected file. All paper-data with identifying information will be stored in locked file drawers, separate from coded data. Documents linking study ID numbers to identifying information will be destroyed at the end of the study. Documents containing data collected on un-consented

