Sharing of data from collaborating sites. Due to the multi-center design of the study, data will be shared with the University of Florida from a collaborating site, the University of Arizona. The collaborating site will send fully de-identified data. Data transfer will take place using the secured infrastructure of the University of Florida RedCap system for questionnaire data. De-identified raw neuroimaging data will be transferred to UF using the Secure File Transfer Protocol (SFTP) onto UF Dropbox servers. A data confidentiality agreement will be signed and filed with the UF IRB before any data are collected at any site.

Storage of collected data. All electronic data are stored in password protected, secured computer systems. All paper data will be stored in a locked file cabinet. Data will only be removed when coded, entered, or audited. Only the participant's study identification number will appear on any data forms. Only the PI, the Co-Is, and the RAs will have access to the completed data forms and electronically stored data. All data are considered part of the participant's confidential record. Data collected from research participants will be stored in a secured, password protected computer file that is separate from network systems. All paper data (e.g., subject contact information, consent forms, etc.) will be placed in a locked file cabinet within 24 hours of their acquisition as designated by the study's RA. All data will remain confidential. Data entry requirements. The data entry system will require a login identification and password in order to gain access to the data. Where appropriate, validation and range rules will be applied to the actual entry fields. Only the PI and Co-Is will be able to view the data in its raw state.

Audit/verification of entered data. All data designated as primary outcome data will be subject to a 100% cross-referencing between electronic and paper forms. This audit must have an error rate less than 1%. If the verification fails the audit, all data will be re-entered, the original computer files discarded, and the newly re-entered data audited. This process will continue until the audit no longer exceeds the maximum allowable error rate. All audits will be supervised and documented by the PI.

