Measurement and reporting of participant accrual and adherence to eligibility criteria. Review of the rate of participant accrual, adherence to inclusion/exclusion criteria will occur weekly during the recruitment phase and then every month to assure that participants meet eligibility criteria and ethnic diversity goals outlined in the grant proposal.

Safety Review Plan Study progress and safety will be reviewed twice per month (and more frequently if needed) by the principal investigator. An annual report will be compiled and will include a list and summary of AEs. In addition, the annual report will address (1) whether adverse event rates are consistent with pre-study assumptions; (2) reason for dropouts from the study; (3) whether all participants met entry criteria; (4) whether continuation of the study is justified on the basis that additional data are needed to accomplish the stated aims of the study; and (5) conditions whereby the study might be terminated prematurely. The IRB and other applicable recipients will review progress of this study annually.

Final storage of paper data. All paper data (e.g., consent forms) may be scanned, and will finally be housed at a facility that specializes in the storage of medical/ research information. The destruction date of these files will be at least 7 years from the termination of the study and will be authorized by the Principal Investigator of the research study.

Access to cleaned computer data. Once the study is complete, and all data have been collected, entered and passed the audit process, the data will be available to the Principal Investigator and his designates for analysis. Only the Principal Investigator can give permission for the release of aggregated study data. No confidential information may be released without

the express written consent of the study participants. Only copies of the finalized data will be released. The original data file will remain in its pristine state.

Description of plan for safety monitoring. Protection of participants from risks related to the study is of paramount concern.

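### Does destroying the ID link when the study ends make the 5- and 10-year driving records unlinkable?

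*Combined protocol and SAP*

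**What the plan says.** The rule on the link is in section 7, Protection against Risk of confidentiality: "Documents linking study ID numbers to identifying information will be destroyed at the end of the study". The same paragraph says the link is held as a password-protected electronic file. No date or event is attached to the study's end, and no group is exempted.

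Section 6.9 (Driving Record Assessment) says that "records will be requested at 5 years post intervention and at 10 years post intervention". It adds that "The driving record assessment is optional", with the choice made at screening.

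Three other places bear on when the study ends, and none defines it:

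- Section 6.18, Timeline: "By Q3 2022 the ACT study is anticipated to be completed and access to the currently blinded randomization conditions will be available". Earlier in section 6.18, the outcome data are to be unblinded only after all of the trial's follow-up visits are done.
- Access to cleaned computer data: release of data follows "Once the study is complete, and all data have been collected, entered and passed the audit process".
- Final storage of paper data: "The destruction date of these files will be at least 7 years from the termination of the study". This covers paper such as consent forms and does not name the electronic link file.

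**The concern.** Read quickly, the two provisions collide. A driving record arrives under a person's name. To use it in a comparison of arms, someone must connect that name to a study ID. Section 7 destroys the file that makes the connection, and the only calendar date the protocol gives for completion of the trial is years before the last driving-record request.

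The documents describe no second route. The central database holds no identities, data forms carry only the study number, and the driver's licence copies of section 6.12 are kept apart from de-identified data. Retained consent forms might still allow a request by name, but the record that came back could not be placed in an arm. Destruction cannot be undone, so a wrong reading would cost the long-term driving outcome for people who had agreed to it.

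**Working it through.** The plan states no figure on this point, so there is nothing to reproduce. The check is date arithmetic under each reading of the study's end, followed by a comparison of the texts.

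**Inputs**

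- Request dates: end of training + 5 years and + 10 years (section 6.9).
- Forecast completion: Q3 2022 (section 6.18).
- Last visit: one year after training (section 6.1).
- Training length: 12 weeks, about 0.25 year (section 6.4).
- In-person work, including tDCS and training, resumes in June 2020 (section 6.17).
- Start of enrolment: not given. The reference list includes 2014 publications, so starts from 2014.0 to 2017.75 were tried as an assumption.

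**Reading 1: link destroyed at Q3 2022**

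A request is in time only if training ended before destruction minus the lag.

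- 10-year requests: Q3 2022 − 10 = Q3 2012. With the earliest assumed start, the first request falls at 2014.0 + 0.25 + 10 = 2024.25. All 10-year requests are late.
- 5-year requests: Q3 2022 − 5 = Q3 2017. Training that ended in June 2020 reaches five years in June 2025, and 2025.45 − 2022.75 = 2.7 years late. At least some 5-year requests are therefore late.
- Share of 5-year requests: with a 2014.0 start the first falls at 2014.0 + 0.25 + 5 = 2019.25, and with a 2017.0 start at 2022.25, both in time. With a 2017.5 start it falls at 2022.75, and with 2017.75 at 2023.0, both at or after destruction. The share runs from some to all, depending on a start date the documents do not give.
- Last requests, assuming the last one-year visit is in Q3 2022: training ends by Q3 2022 − 1 = Q3 2021, so the last 5-year request is Q3 2026 and the last 10-year request is Q3 2031.

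**Reading 2: the study ends when its scheduled data collection ends**

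The link is kept until about Q3 2031, which is Q3 2031 − Q3 2022 = 9 years beyond the forecast date. No request is late.

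**Which reading fits the texts**

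Section 6.18 attaches Q3 2022 to access to the randomisation conditions, and makes that access wait for the follow-up visits. Taken together, the date marks the end of visits. A request for driving records is not a visit. Section 6.18 also places its Aim 2 and exploratory aim after that access, so work under the protocol continues past the date. No sentence connects this milestone to the link file.

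Section 6.9, by contrast, is part of the protocol's own Research Plan. The data-access text pairs completion of the study with all data having been collected. That is not a definition, but it supports Reading 2 at least as well as section 6.18 supports Reading 1.

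The 7-year rule settles nothing either way, because it concerns paper files.

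**The case for a change.** The best case for acting is that the early reading is not perverse. Section 6.18 does call the trial complete at Q3 2022. The three primary time points in section 6.1 stop at one year, and the plan in section 7 for keeping in touch with participants stops at the one-year visit. A data manager working only from the confidentiality paragraph could destroy the link then, and the loss would be permanent. A sentence of clarification would cost little. Keeping everyone's link until the last request has its own price: people who declined the driving records would stay identifiable for up to about 9 years longer than under the early reading.

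What stands is that the term is undefined and the arithmetic under Reading 1 is right. What does not stand is the step from an undefined term to a defect in the plan. The harm requires the team to destroy a file that it needs for requests in its own protocol, on the strength of a forecast made for unblinding. The privacy cost for those who declined is a matter of careful file-keeping and does not affect inference. The consent form and the manual of procedures may also set retention terms for this optional component; neither was available to check.

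**Conclusion.** This is a gap that the investigators would fill sensibly, and no change to the plan follows. The study's end is left undefined for the link file, but the ordinary meaning of the term leaves the scheduled driving-record requests inside the study, and on that meaning none is affected. Only if the link were destroyed at about Q3 2022 would all 10-year requests and at least some 5-year requests be lost to linkage.

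The number of participants at risk cannot be computed, since opt-in counts and enrolment dates are not given. The dates of the last requests rest on the assumption that the last one-year visit falls in Q3 2022. Even in the worst case the loss is confined to the optional driving outcome: the NIH Toolbox primary outcome and the aims and hypotheses in section 5 do not draw on driving records.
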